## 1. RESEARCH REFERENCE NUMBERS

Sponsor Protocol Number:	PID: 18505
Clinical Trials Unit (CTU) Reference:	OCTRU375
Funder Reference:	NIHR134859
Ethics Reference Number:	25/EE/0040
IRAS Number:	343826
Registry:	International Standard Randomised Controlled Trial Number (ISRCTN): tbc

#### 5. LAY SUMMARY/PLAIN ENGLISH SUMMARY

#### Why are we doing this research?

Low back pain is common and often improves without specific treatment. Where it doesn't, painkillers and physiotherapy can be successful and previous research has shown this is the best initial treatment. However, this approach does not work for everyone, and some people are left with persistent, severe low back pain impacting their health, daily activities and work. The cause of more persistent low back pain is thought to be 'wear-and-tear' (degeneration) of the spinal joints in the lower back. Spinal fusion, an operation that surgically fixes the spinal bones together in that area, may help. This type of fusion operation has been used successfully for degenerative conditions in the ankle and wrist, but its benefit remains less clear for patients with low back pain and degeneration.

We want to find out if spinal fusion surgery for a carefully selected group of patients with persistent severe low back pain, and who have already undergone non-surgical treatment, is more beneficial than continuing with best conservative (non-surgical) care. Best conservative care is an agreed patient focused treatment plan combining the use of medication, exercise, and pain control strategies. We also want to find out if the surgery is good value for money for the NHS.

#### How will the research be done?

A special type of study called a randomised controlled trial is needed to answer this question. This involves assigning participants to different treatments using a process called randomisation so the effects of each treatment can be compared fairly. After giving consent, 270 participants will be included and will have an equal chance of being allocated to receive either fusion surgery or best conservative (non-surgical) care (135 per group). Participants allocated to best conservative care will have some "tailoring" of their care (to make it the very best possible). Over a 24-month period we will ask participants about their physical function, pain, mental health, general health, quality of life, days off work and healthcare use. We also plan longer-term follow-up (at 5 years) if funding can be secured.

#### Who has been involved in the design of the project?

A PPI (Patient and Public Involvement) group of 8 patients has helped the study team shape the study, including having had five specific PPI meetings. A trial specific PPI group continue to input in the delivery of this study, this includes patients with experience of long-term, severe low back pain and fusion surgery. One is also a co-applicant on the study. Two other patient representatives sit on the Trial Steering Committee, which is a key oversight group for the study.

#### How will the results of this research be used?

At present lumbar spine fusion for low back pain is used rarely within the NHS. This study will provide evidence to guide decisions for patients and doctors about whether such surgery should be offered in the future to carefully selected patients with ongoing and severe low back pain. The findings will be made available to patients and the public, clinicians, healthcare managers, commissioners and national bodies (via spinal healthcare organisations, charities and policy-making such as the National Back Pain Pathway and NICE guidelines).

#### Who are the research team?

FORENSIC-UK has been designed by a team of spinal surgeons, physiotherapists, patients, pain specialists, researchers, statisticians, and health economists from several universities and hospitals, including Oxford, Cardiff, Keele, Sheffield, Birmingham, Bristol, Leeds, Southampton, Frimley, and

University College London. An Australian research group is also involved and conducting a very similar study to the same protocol (a 'sister' study known as FORENSIC-Australia).

## 6. STUDY SYNOPSIS

Full Study Title:	The clinical and cost-effectiveness of lumbar fusion surgery for patients with persistent, severe low back pain (LBP)		
Short Title:	FusiOn veRsus bEst coNServative Care (the FORENSIC-UK trial)		
Study Acronym:	FORENSIC-UK		
Study Design:	A multicentre, 2 arm superiority RCT with internal pilot, integrated QRI and health economic analysis. Participants will be randomised (1:1) to either Lumbar Fusion Surgery (LFS) or continued Best Conservative Care (BCC).		
Study Participants/Target Population:	Adults aged 18 to 65 with persistent severe Lower Back Pain (LBP) with recent imaging evidence of lumbar degeneration who have already undergone previous conservative treatment.		
Eligibility criteria	

Aged 18 to 65.

		
	
 
Episode of Low Back Pain (lasting ≥6 months).
 
Low Back Pain is ≥6 on a 0-10 Numerical Rating Score (NRS).
 
Have undergone previous non-surgery treatment that aligns with best practice guidelines, (National Institute of Health and Care Excellence. Low back pain and sciatica in over 16s: assessment and management (Clinical Guideline [NG59]) London 2016. Sect. 1.9) e.g. 
 
a course of physical therapy
 
a course of psychological therapy
 
a course of treatment from a multi-disciplinary team
 
a course of treatment from specialist medical care
 
Medial branch blocks/radiofrequency denervation
 
Analgesia
 
 
 
		
	
 
Willing and able to provide informed consent.
 
Recent evidence (within the last 12 months) of lumbar degenerative disease using appropriate imaging (Magnetic Resonance Imaging [MRI] +/- Single Photon Emission Computed Tomography/Computed Tomography [SPECT/CT), +/- previous discectomy/decompression.
 
Suitable for both lumbar fusion surgery (LFS) at 1 or 2 lumbar spine levels and best conservative care (BCC).
 
		
	Exclusion:		
	
 
Has low-back related leg pain more severe than low back pain e.g.: Claudication.
 
Pain in any other body region more severe than low back pain
 
		

	
 
Previous (or attempted) LFS.
 
Has psychiatric disorders (e.g. diagnosed personality disorders, post-traumatic stress disorder, drug or alcohol abuse/addiction, diagnosis of severe depression).
 
Radiculopathy or claudication or clinical signs of nerve decompression where the treatment plan includes offering a direct or indirect decompression along with the fusion.
 
Any other reasons indicated for lumbar fusion surgery (LFS) e.g. deformity, infection, tumours, instability (due to spondylolisthesis of grade 2 or above), spinal fracture, systematic inflammatory disease.
 
		
No. of study arms	Two		
Intervention	Lumbar Fusion Surgery [LFS] (&	post-ope	rative care)
Comparator	Best Conservative Care (BCC)		
Planned Sample Size:	270 participants (135 per arm)		
Target no. of centres:	Approximately 20 UK NHS Hospitals		
Planned recruitment duration:	Recruitment is expected to last for 24 months		
Duration of intervention/treatment:	Intervention: Lumbar Fusion Surgery [LFS] and inpatient stay (& post- operative care and physiotherapy)		
	Comparator: Best Conservative Care (BCC)		
Follow-up duration:	Each participant will be followed up for 24 months from randomisation.		
	Objectives Outcome Measures		
Primary objective and outcome measure:	1) To test for superiority of lumbar fusion surgery versus continued best conservative (non- surgical) care on disability (physical function) in patients with severe persistent LBP and lumbar degenerative disease.		LBP-related physical function using the Oswestry Disability Index (ODI) at 24 months post randomisation.
Secondary objectives and outcome measures:	2) To investigate the cost- effectiveness of lumbar fusion surgery compared with continued best conservative care.		
	Refer to the OBJECTIVES AND OUTCOME MEASURES section of the main protocol for full study objectives and outcome measures.		
QuinteT Recruitment Intervention (QRI/Information Study	
 
To understand the recruitment process in the FORENSIC-UK Study (Phase 1).
 
	The QRI team will present a summary of anonymised findings emerging from the QRI, based upon:	

in patient facing documents)	
 
To develop strategies to optimise recruitment and informed consent (Phase 2).
 
	1(a). Analysis of screening log data, audio recordings of recruitment appointments and interviews with the TMG, recruiters and potential participants for FORENSIC-UK.
		1(b). Results from the mapping of recruitment processes at FORENSIC-UK study sites.
		2(a). Suggestions will be made to change aspects of design, conduct, organisation or training.

#### 7. ABBREVIATIONS

ACT	Acceptance and Commitment Therapy
ACT	Adverse Event
AR	Adverse Event Adverse Reaction/Response
AX Hub	Adverse Reaction/Response Axial Spondylarthritis Clinic
BAME	Black and Asian Minority Ethnic
	· · · · · · · · · · · · · · · · · · ·
BCC	Best Conservative Care
BMP	Bone Morphogenic Protein
BSR	British Spine Registry
CA	Conversation Analysis
CAG	Clinical Advisory Group
CATS	Clinical Assessment and Triage Services
CI	Chief Investigator
CMATS	Clinical Musculoskeletal Assessment and Treatment Service
CONSORT	Consolidated Standards of Reporting Trials
CRF	Case Report Form
CSF	Cerebrospinal Fluid
СТ	Computed Tomography
CTU	Clinical Trials Unit
DSMC	Data and Safety Monitoring Committee
DVT	Deep Vein Thrombosis
EQ-5D-5L	European Quality of Life- 5 Dimensions - 5 Level version
FORENSIC	FusiOn veRsus bEst coNServative Care
GCP	Good Clinical Practice
GDPR	General Data Protection Regulation
GPE	Global Perceived Effects
GP	General Practitioner
НСР	Health Care Professional
HEAP	Health Economic Analysis Plan
HES	Hospital Episode Statistics
HRA	Health Research Authority
HRG	Healthcare Resource Group
iCAT	Integrated Clinical Assessment and Treatment
ICF	Informed Consent Form
ICMJE	International Committee of Medical Journal Editors
IMD	Index of Multiple Deprivation
IMMPACT	Initiative on Methods, Measurement, and Pain Assessment in Clinical Trials
ISF	Investigator Site File
ISRCTN	International Standard Randomised Controlled Trials Number
LBP	Lower Back Pain
LFS	Lumbar Fusion Surgery
MCID	Minimal Clinically Important Difference
MedDRA	Medical Dictionary for Regulatory Activities
MDT	Multi-Disciplinary Team
MSK	Musculoskeletal Service
NG59 GDG	NICE Guidelines – Guideline Development Group
NHS	National Health Service
NICE	National Institute for Health and Care Excellence

NIHR	National Institute for Health and Care Research
NLBRPP	National Low Back Pain and Radicular Pain Pathway
NRS	Numerical Rating Score
MCAT	Musculoskeletal Clinical Assessment and Triage
OCTRU	Oxford Clinical Trials Research Unit
ODI	Oswestry Disability Index
PE	Pulmonary Embolism
PI	Principal Investigator
PIC	Participant Identification Centres
PIS	Participant Information Sheet
PPIE	Patient and Public Involvement and Engagement
PSEQ	Pain Self Efficacy Questionnaire
PHQ 8	Patient Health Questionnaire 8-item
QA	Quality Assurance
QALY	Quality Adjusted Life Year
QC	Quality Control
QRI	QuinteT Recruitment Intervention
RCT	Randomised Controlled Trial
RDSF	Research Data Storage Facility
REC	Research Ethics Committee
RSI	Reference Safety Information
SAE	Serious Adverse Event
SEAR	The Screened, Eligible, Approached, Randomised Framework
SAP	Statistical Analysis Plan
SDM	Shared Decision Making
SDV	Source Data Verification
SITU	Surgical Intervention Trials Unit
SMS	Short Message Service
SOC	System Organ Class
SOP	Standard Operating Procedure
SPECT	Single-Photon Emission Computerised Tomography
SPIRIT	Standard protocol Items: Recommendations for Interventional Trials
TIDieR	Template for Intervention Description and Replication
TMF	Trial Master File
TMG	Trial Management Group
TSC	Trial Steering Committee
ТЅК	Tampa Scale of Kinesiophobia
UKSSB	United Kingdom Spine Societies Board

#### 8. BACKGROUND INFORMATION AND RATIONALE

Lumbar fusion is an operation to fix vertebrae and use bone graft to achieve fusion. It is included in the National Institute for Health and Care Excellence (NICE) guidelines  and the National Low Back and Radicular Pain Pathway (NLBRPP). However, its effectiveness for lower back pain (LBP) associated with lumbar degenerative changes compared to conservative care is unclear, leading to NICE  stating in 2016 that it should only be used in a randomised controlled trial (RCT). There were 4000 fusions in the NHS in 2009/10 reducing to < 1000 in 2018/19 (Hospital Episode Statistics (HES) data). In the NLBRPP, spinal fusion is included only as an option if patients have failed non-surgical treatments (currently, given NICE's statement, fusion surgery is not an option for these patients in the UK). We do not know if this surgery is beneficial or cost effective for this patient group because previous studies have weaknesses which include high cross-over rates, heterogeneous populations, and varied approaches to conservative care.

Worldwide, LBP is the leading cause of disability with highest burden from persistent, severe LBP. Whilst the Lancet LBP Series highlighted past errors of over-reliance on medications and surgery  the current UK situation (lack of quality rehabilitation programmes and the decommissioning of LFS) has left a substantial cohort of patients in difficulty. The NIHR has identified that LFS may be an option but requires evaluation as it is expensive and has risks. LFS may be better than continued best conservative care (BCC) [non-surgical] for these patients who have failed to improve with previous conservative treatments and who are considered appropriate patients for lumbar fusion surgery. It is crucial that patients have tried recommended conservative treatments before they are considered for spinal fusion, thereby reserving LFS for patients who have not had good response from previous conservative care. LFS may be better than BCC for appropriate patients with specific characteristics.

The few RCTs that have compared LFS to non-surgical care for LBP  are limited by small samples, cross-over, selection bias and widely varying non-surgical care. Studies  conclude no clear advantage of fusion but show modest benefits for function, pain and general health. The only previous UK trial  concluded there was no clear evidence that LFS was better than intensive rehabilitation although the trial included a mix of patients with chronic LBP, including those with spondylolisthesis and previous laminectomy surgery. That trial changed practice, and better quality conservative treatment pathways now exist (but are not always readily available), and no work has examined the more contemporary issue of whether LFS has a place in treating patients who have not responded to recommended conservative care interventions. The most recent systematic review  and meta-analysis of 6 RCTs concluded LFS is no better than non-operative care for pain and disability at short, or long term follow-up. It also concluded that previous RCTs had relatively 'lax' patient inclusion criteria and advised future RCTs to better define their selection criteria.

#### 9. OBJECTIVES AND OUTCOME MEASURES

#### 9.1. Aim

The aim of the FORENSIC-UK study is to assess if lumbar fusion surgery (LFS) is more clinically and cost effective than continued best conservative care (BCC) for people with persistent lower back pain (LBP) and lumbar degenerative disease as measured by a validated LBP disability score (Oswestry Disability Index) at 24 months follow-up.

Our objectives are:

1) To test for superiority of LFS versus BCC on disability (physical function) in patients with persistent LBP.

2) To investigate the cost-effectiveness of LFS compared with BCC.

A Quintet Recruitment Intervention (QRI) is also included with the following objectives:

- 1) To understand the recruitment process in the FORENSIC-UK study
- 2) To develop strategies to optimise recruitment and informed consent

#### 9.2. Primary and secondary objectives and outcome measures

The primary outcome is the Oswestry Disability Index (ODI), a validated LBP physical function disability score, at 24 months (also measured at 6 & 12 months). The ODI is well validated and a commonly used outcome measure in LBP RCTs including surgery and contains 10 items that assess domains including personal care, walking, standing and sleeping.

Secondary outcomes include LBP severity (Numerical Rating Scale), measured using monthly SMS data or by email or paper options dependant on participant preference (over 24 months). We will also collect participant reported outcome measures reported via questionnaires at 6, 12 and 24 months. The participant questionnaires include: quality of life (EQ-5D-5L), depression (PHQ8), fear avoidance beliefs (TSK), pain self-efficacy (PSEQ), work outcomes (days-off-work), comparison of back pain from entering the study to timepoint of questionnaire using Global Perceived Effect Scale (GPE), healthcare use (NHS and non-NHS including concurrent treatments ie: analgesia) and treatment satisfaction measured at 24 months follow-up with scoring 0-10 (with 10 being very satisfied with treatment).

Further secondary outcome measures will be collected throughout the 24 months using specially designed CRF's to be completed by clinicians and researchers regarding surgery, Best Conservative Care (BCC), Surgery complications (intra and post operative), further surgery including re-admission, Fusion Failure (LFS participants only), BCC complications.

Objective	Outcome measure	Time point(s) of evaluation of this outcome measure (if applicable)
1. To test for superiority of	Primary:	24 months (also measured at 6
lumber fusion surgery (LFS)	LBP-related physical function	& 12 months)
versus BCC on disability	using the Oswestry Disability	
(physical function) in	Index (ODI version 2.1b)	
patients with persistent		
lower back pain (LBP)		
	Secondary:	
2. To investigate the cost-		
effectiveness of LFS	LBP severity (Numerical	
compared with best	Rating Scale) monthly – post	
conservative care (BCC)	randomisation	
	Participant reported	
	outcomes	

	measured at 6m, 12m and	
	24m post randomisation:	
	1. Quality of Life: EQ-5D-5L	
	2. Pain Self-efficacy	
	Questionnaire (PSEQ)	
	3. Patient Health	
	Questionnaire (PHQ8)	
	4. Tampa Scale of	
	Kinesiophobia (TSK)	
	5. Global Perceived Effect	
	Scale (GPE)	
	6. Healthcare Resources	
	Use	
	7. Work status	
	8. Treatment Satisfaction	
	at 24m Follow up only	
	Additional outcome	
	measures:	
	9. Complications Data (inc.	
	re-admissions)	
	,	
QuinteT Recruitment Intervent		
QuinteT Recruitment	1.To understand the	The QRI team will present a
Intervention (QRI or	recruitment process in the	summary of anonymised
Information Study in patient	FORENSIC-UK Study	findings emerging from the
facing documents)	(Phase 1).	QRI, based upon:
		1(a). Analysis of screening log
		data, audio recordings of
		recruitment appointments and
		interviews with the TMG,
		recruiters and potential
		participants for FORENSIC-UK.
		1(b). Results from the
		mapping of recruitment
		processes at FORENSIC-UK
		study sites.
		study sites.
	2. To develop strategies to	2(a). Suggestions will be made
	optimise recruitment and	to change aspects of design,
	informed consent	conduct, organisation or
	1	
	(Phase 2).	training.

#### 9.3. Choice of primary outcome

The Oswestry Disability Index (ODI) is a well validated and commonly used outcome measure in low back pain (LBP) RCTs including surgery, contains 10 items that assess domains including personal care, walking, standing and sleeping.

Follow-up at 24 months after randomisation allows participants in both arms to reach at least 1 year follow-up after intervention taking into account treatment waiting lists.

#### 9.4. Use of core outcome sets

The outcomes included in this trial reflect the core outcome sets for LBP RCTs, and Initiative on Methods, Measurement, and Pain Assessment in Clinical Trials (IMMPACT) guidance.

#### 9.5. Exploratory objectives/additional mechanistic objectives outcomes

There are no additional exploratory/mechanistic objectives/outcomes in this study.

#### **10. STUDY DESIGN AND SETTING**

The study is a multicentre, 2 parallel arm (lumber fusion surgery (LFS) versus best conservative care (BCC) [control]), superiority RCT with an internal pilot, integrated QuinteT Recruitment Intervention (QRI) and health economic analysis. The design is pragmatic and accounts for the main study purpose (to assess clinical and cost effectiveness of LFS in the contemporary NHS setting) whilst accounting for the current NICE guidance for persistent LBP.

270 participants (135 per arm) will be recruited from approximately 20 sites in the UK. Participants will be randomised to receive lumber fusion surgery or best conservative care.

A study flow chart is provided in APPENDIX 1 – study FLOW CHART.

Prior to study enrolment, all potential participants will have undergone core conservative therapies recommended in national guidance, such as exercise therapy, analgesia, and/or a psychologically informed LBP programme. Core therapies may have been delivered virtually, face to face, individually or in a group.

All participants will be suitable for both LFS and BCC. Patients with neurological symptoms for which a surgeon would rather consider decompression surgery due to lumbar spine deformity, lumbar spine infection, tumours, spondylolisthesis of grade 2 or above, spinal fracture, systemic inflammatory disease or previous fusion surgery, will be excluded. Those who have pain in multiple body sites, where the LBP is not the priority pain problem, will also be excluded.

Recruitment to the study will occur following discussion between a potential participant and review of the eligibility criteria by a participating surgeon at an outpatient clinic appointment in secondary care. As outlined earlier in Section 8, as LFS in not available as a treatment option for this group in the NHS apart from when used in an RCT, patients will not currently be routinely referred to secondary care for surgeon review for LFS. Therefore, potential eligible participants will need to be identified in various other parts of the patient pathways e.g. Musculoskeletal Clinical Assessment and Triage/ Integrated Clinical Assessment and Treatment (MCAT/iCAT) services, community physiotherapy centres, GP's and Primary Care and be referred through where appropriate to secondary care. We will also recruit from Orthopaedic centres and Neurosurgery centres in secondary care. If eligible participants wish to participate in the study and provide written consent, following baseline data collection they will then be randomised to either: (1) Lumbar Fusion Surgery (LFS & usual post-operative care) or (2) Best Conservative Care (BCC).

Participants randomised to LFS will be listed and undergo spinal fusion surgery at one or two lumbar spine levels as determined by the opinion of the surgeon performing the operation. Any standard accepted fusion method/graft option is allowed, except the use of bone morphogenic protein (BMP), to maximise external validity.

BCC will commence with a review by a senior spinal practitioner or pain physician (usually a musculoskeletal physiotherapist) experienced in assessing and treating LBP with links to a wider multidisciplinary team. Following this review, participants will be offered a package of personalised BCC, based on the participant's individual goals, abilities, and expectations. The content of BCC includes non-surgical interventions recommended by NICE, the National Low Back and Radicular Pain Pathway (NLBRPP), and approved by our Clinical Advisory Group (CAG) (see Section 13).

#### **10.1.** Internal pilot/Decision points

The embedded pilot phase will take place in 10 sites with staggered initiation over a period of 10 months. The overall participant recruitment target for this period will be 45 (site recruitment target rate of 1-2 participants per month). The aim of the pilot will be to assess the recruitment strategy, modifying as appropriate. The internal pilot phase will use progression criteria (stop/amend/go). Each item will be assigned red, amber, or green to represent performance. The Trial Management Group (TMG) and Trial Steering Committee (TSC) will review the results of the pilot phase to determine further trial progression (stop/amend/go) and need for further site support or protocol amendments.

The internal pilot phase will mirror the procedures and logistics undertaken in the main definitive trial. It is intended that the trial will progress seamlessly into the main phase, with internal pilot phase participants included in the final analysis. This pilot phase will also confirm the expected rate of recruitment for the main trial phase. Following this internal pilot phase, additional sites (anticipate being up to 20 in total) across the UK will then be opened to recruitment to reach the overall target sample size of 270 participants.

Progression criteria	Red	Amber	Green
Trial recruitment % complete of total for internal pilot (n=45)	<60%	60%-99%	100%
Total number of participants recruited	<27	27-45	>45
Recruitment rate/site/month*	0.5	0.5-0.75	>0.75
Number of sites opened in 10 months	<6	6-9	10

Table 1 : Progression criteria (stop/amend/go criteria) for the internal pilot phase

NB: \* = individual sites will vary, and figures are means across sites. The values are given in the metrics requested by the funder, viz. rate of participants per site per month.

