## 10.11. Expected recruitment rate.

The anticipated monthly recruitment rate is 1 participant per month per site after the initial pilot. There will be a phased introduction to the opening of sites, and it is expected that all sites will be open within 15 months of starting recruitment. Each of the 20 NHS Trusts (and community partners) planned to take part in the FORENSIC-UK study currently manage patients in Clinical Musculoskeletal Assessment and Treatment Service CMATS clinics, pain clinics, spine clinics, primary care clinics, via GP surgeries or with first contact practitioners. The recruitment rate for the study was conservatively estimated to allow for the implementation of the trial into current pathways and pressures on resources within the NHS.

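### The internal-pilot table gives two colours at its own target of 45, and its green rate floor of 0.75 per site per month is not reconciled with 270 participants in 24 months

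*Protocol*

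**What the plan says.** Protocol section 10.1 describes the pilot: "The embedded pilot phase will take place in 10 sites with staggered initiation over a period of 10 months". Its goal is stated as "The overall participant recruitment target for this period will be 45 (site recruitment target rate of 1-2 participants per month".

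Three rows of Table 1 matter here:

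- Row 1, headed "Trial recruitment % complete of total for internal pilot (n=45"), is red below 60%, amber from 60% to 99% and green at 100%.
- Row 2 reads "Total number of participants recruited <27 27-45 >45" (red, amber, green).
- Row 3 reads "Recruitment rate/site/month* 0.5 0.5-0.75 >0.75" (red, amber, green). Its footnote says that the figures are averages over sites.

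Each item gets its own colour, and the Trial Management Group and Trial Steering Committee then review the results. Section 10.1 adds a forecasting purpose: "This pilot phase will also confirm the expected rate of recruitment for the main trial phase". After the pilot, "additional sites (anticipate being up to 20 in total) across the UK will then be opened to recruitment to reach the overall target sample size"; that target is 270.

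Section 10.11 states the planning rate: "The anticipated monthly recruitment rate is 1 participant per month per site after the initial pilot". It expects phased opening, with every site open by month 15. The synopsis gives 24 months of recruitment. Section 22.2 bases the 270 on a difference of 8 ODI points, SD 18, two-sided 5%, 90% power and 20% loss.

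**The concern.** Rows 1 and 2 measure the same thing, once as a percentage of 45 and once as a number, so they should agree everywhere. They agree at the lower cut (60% of 45 is 27) but not at the upper one. The value where they part is the pilot target itself. If the pilot lands there, the colour would have to be chosen after the data are known.

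The rate row raises a second question. The pilot is meant to confirm the main-phase rate, yet green on that row starts below the rate the protocol plans for. If 0.75 is also below what 270 in 24 months requires, a green there does not show that the sample size behind the 90% power is within reach.

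**Working it through.** **1. Rows 1 and 2 side by side**

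| Recruited | % of 45 | Row 1 | Row 2 |
|---|---|---|---|
| 26 | 57.8 | red | red |
| 27 | 60.0 | amber | amber |
| 44 | 97.8 | amber | amber |
| **45** | **100.0** | **green** | **amber** |
| 46 | 102.2 | green | green |

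The conflict is confined to one value, 45.

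**2. The plan's own figures**

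- Sample size: with difference 8 and SD 18, the t-based requirement is 107.4, so 108 per arm. 108 / 0.8 = 135 per arm, 270 in total. This reproduces.
- Pilot target: recruits = open site-months × rate. If one of the 10 sites opens each month, there are 45 site-months (openings at month end), 50 (continuous) or 55 (month start). At 1 per site per month these give 45, 50 and 55, so the target of 45 reproduces at the low end.

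**3. Site-months after the pilot (assumed, since no calendar is given)**

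- Central: 10 to 20 sites evenly over months 10 to 15, then 20 sites for 9 months: 5 × 15 + 9 × 20 = 255.
- Fast: all 20 open at month 10: 14 × 20 = 280.
- Slow: the extra 10 open only at month 15: 5 × 10 + 9 × 20 = 230.

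**4. Total by month 24, starting from 45 pilot recruits**

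Total = 45 + rate × site-months. Rate needed = (270 − 45) / site-months = 225 / site-months. Overrun = shortfall / (20 × 0.75) = shortfall / 15 months.

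| Schedule | At 0.75 | Shortfall | Overrun (months) | At 1.0 | Rate needed |
|---|---|---|---|---|---|
| Slow (230) | 217.5 | 52.5 | 3.5 | 275 | 0.98 |
| Central (255) | 236.25 | 33.75 | 2.25 | 300 | 0.88 |
| Fast (280) | 255 | 15 | 1 | 325 | 0.80 |

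**5. Power if recruitment stopped at month 24**

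Two-sample t-test, difference 8, SD 18, two-sided 5%, 80% retained:

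- 217 randomised: 83%
- 236 randomised: 86%
- 255 randomised: 88.5%
- 270 randomised: 90%

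**6. What the count rows imply about the rate**

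Reaching 45 in 45 to 55 site-months means 45/55 = 0.82 to 45/45 = 1.0 per site per month. At 0.75 the pilot would recruit 0.75 × 45 = 34 to 0.75 × 55 = 41, which is amber on both count rows.

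**The case against.** The case against giving this much weight has several parts.

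- **One value, and a judged decision.** The row 1 and row 2 clash affects only 45, and two committees review the colours. That limits the consequence. It does not make the two rows consistent.
- **The rate row's red cell.** As printed, exactly 0.5 has two colours and anything lower has none. The other three red cells shown in the table carry a less-than sign, so one was probably lost here, perhaps only in conversion from PDF. This is something to confirm and should not be counted as an error.
- **Different colours on count and rate.** A reader might call this a further contradiction. It is not: they are separate items, graded separately, and such tables often show mixed colours.
- **The green rate.** A reader might infer that the green criterion fails to deliver 270. The protocol does not support that. More than 0.75 is a floor, and green includes the planned rate of 1, which gives 275 to 325. Even a pilot run at 0.75 throughout (about 38 recruits on 50 site-months) followed by 1 per site per month over 255 site-months gives about 38 + 255 = 293.
- **The rate row does not stand alone.** The count rows ask for an implied 0.82 to 1.0 under staggered opening, so a pilot at 0.75 would be green on the rate row only.
- **Power.** The loss arises only if recruitment closes at month 24. The synopsis gives 24 months as an expectation, and an extension would restore the 270.

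What remains is narrower: the protocol gives no reason for a green floor below its planning rate, and does not say what rate must follow.

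**Conclusion.** The contradiction at 45 is certain and rests on nothing beyond the table itself. It is small in extent, but it sits on the target of a stop/amend/go rule and should be corrected before pilot data are seen.

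The rate point holds in a limited form: a green on that row alone does not confirm a main-phase rate that reaches 270 in 24 months. The rate needed is about 0.88 (range 0.80 to 0.98), above 0.75 in every schedule examined. A sustained 0.75 gives about 236 (range 217 to 255), with about 86% power (range 83% to 88.5%) if recruitment stopped there, or an overrun of about 2 months (range 1 to 3.5). These figures assume 45 pilot recruits, 230 to 280 later site-months, the 0.75 rate persisting, and the protocol's own difference, SD and loss. The sample size of 270 is not in question.

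**What to change.** 1. Change row 2 of Table 1 to <27 / 27–44 / ≥45, so that it matches row 1.
2. Confirm that the red cell of the rate row reads <0.5, and restore the sign if it is missing.
3. Reconcile the green rate with sections 10.1 and 10.11 in one of two ways. Either set it at the rate the trial's actual opening schedule needs for 270 in 24 months, or keep 0.75, label it a start-up allowance, and print beside it the post-pilot rate then required (about 0.88 on the central schedule here; the team should use its own calendar).

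The cost is the wording of one table in a protocol amendment. The downside is a green criterion that is slightly stricter, or more explicit about what must follow. Participant procedures, the analysis and the sample size do not change.
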